Appendix 3:

Egg Beaters Gastric Emptying Scintigraphy

Items needed for Egg Beaters Gastric Emptying Scintigraphy:

118 mL of liquid egg whites (Egg Beaters; egg substitute): 99% real eggs, cholesterol free, fat free, low calorie (120 g Egg Beater, 60 kcal, **approx. two large eggs**), 2 slices of wheat bread (120 kcal), Strawberry jam (30 g, 74 kcal) Water (120 ml). Technetium-99m 0.75 mCi

To prepare the meal, 0.75 Ci of 99Tc sulfur – colloid is mixed with liquid egg whites, the mixture is cooked in a microwave or on a hot nonstick skillet. The Egg Beater mixture is stirred once or twice during cooking and is cooked until it has the consistency of an omelet (3-5 min). The bread is toasted. Jelly is spread on the bread, and a sandwich is made of the jellied bread and cooked egg mixture. The subject completes the sandwich meal quickly, within max. 10 minutes.

Gastric emptying studies are generally performed in the morning. Patient should be fasting overnight or for at least 6 hours. Patients should generally stop prokinetic agents, and anticholinergic agents that can affect gastric emptying for 3 days prior to the test. should have a reasonable glucose level for the test. Generally, the fasting glucose in diabetic patients should be between 75 and 275 mg/dL (4.2 to 15.3 mmol/l). Diabetic patients should self-administer their insulin with meal ingestion, generally ½ what they take normally. The nutritional composition of the meal is 69-72% carbohydrate, 22-24% protein, 2% fat and 2% fiber. Other alternative meals may also be useful for patients with egg allergies or intolerance to eggs, and patients with gluten-sensitive enteropathy according local principles.

Gastric Emptying of Solids 13C-Octanoic Acid Breath Test (Leuven Model)

The test is performed after an overnight fast.

A dose of 100 mg (1- 13 C)-Octanoic Acid is administered orally in a solid test meal. The test meal is standardized and consists of one scrambled egg with two slices of white bread and 5 g of margarine, together with 150 ml water (swallowed immediately after ingestion of the meal). The total caloric content is 250 kcal. The egg yolk is doped with 100 mg (1- 13 C)-Octanoic Acid and fried separately from the egg white. The meal is consumed within 10 minutes.

Breath samples are collected before (2x), every 5 minutes during the first 30 minutes (0.5 h) and every 15 minutes for the next 210 minutes (3.5 h) after the ingestion of the (1-\frac{13}{C})-Octanoic Acid. \frac{13}{C} enrichment in breath CO2 is determined by Isotope Ratio Mass Spectrometry (IRMS). The equation of the breath test results is obtained by 2 non-linear regression curves fitting the % dose \frac{13}{C} recovered in breath per minute and the cumulative % dose recovered in breath. From this equation the half emptying time and the lag phase time are calculated as well as the gastric emptying coefficient (GEC).

Appendix 4

The PAGI-QOL (Quality of Life Questionnaire)

The following questions ask about how some of the gastrointestinal problems you may be experiencing (such as pain, discomfort or other problems) may have affected your overall quality of life and well-being in the past 2 weeks.

Please answer every question by circling the number that best represents your opinion. There are no right or wrong answers

right or wrong answers.		1			1 22 . 63	177 0.7
During the past 2 weeks, because of your gastrointestinal problems, how often	None of the time	A little of the time	Some of the time	A good bit of the time	Most of the time	All of the time
1. have you had to depend on others to do your daily activities?	0	1	2	3	4	5
2. have you avoided performing your daily activities?	0	1	2	3	4	5
3. have you had difficulty concentrating?	0	1	2	3	4	5
4. has it taken you longer than usual to perform your daily activities?	0	1	2	3	4	5
5. have you felt tired?	0	1	2	3	4	5
6. have you lost the desire to participate in social activities such as visiting friends or relatives?	0	1	2	3	4	5
7. have you been worried about having stomach symptoms in public?	0	1	2	3	4	5
8. have you avoided performing physical activities or sports?	0	1	2	3	4	5
9. have you avoided traveling?	0	1	2	3	4	5
10. have you felt frustrated about not being able to do what you wanted to do?	0	1	2	3	4	5
11. have you felt constricted in the clothes you wear?	0	1	2	3	4	5
12. have you felt frustrated about not being able to dress as you wanted to?	0	1	2	3	4	5
13. have you felt concerned about what you can and cannot eat?	0	1	2	3	4	5
14. have you avoided certain types of foods?	0	1	2	3	4	5
15. have you restricted eating at restaurant or at someone's home?	0	1	2	3	4	5
16. have you felt less enjoyment in food than usual?	0	1	2	3	4	5
17. have you felt concerned that a change in your food habits could trigger your symptoms?	0	1	2	3	4	5
18. have you felt frustrated about not being able to choose the food you wanted to?	0	1	2	3	4	5
19. have you left frustrated about not being able to choose the type of beverage you wanted to?	0	1	2	3	4	5
20. has your relationship with your spouse or partner been disrupted?	0	1	2	3	4	5
21. has your relationship with your children or relatives been disrupted?	0	1	2	3	4	5
22. has your relationship with your friends been disrupted?	0	1	2	3	4	5
23. have you been in a bad mood?	0	1	2	3	4	5
24. have you felt depressed?	0	1	2	3	4	5
25. have you felt anxious?	0	1	2	3	4	5
26. have you felt angry?	0	1	2	3	4	5
27. have you felt irritable?	0	1	2	3	4	5
28. have you felt discouraged?	0	1	2	3	4	5
29. have you been stressed?	0	1	2	3	4	5
30. have you felt helpless?	0	1	2	3	4	5

The PAGI-QOL contains 30 items with five subscales:

- (1) daily activities (1 10)
- (2) clothing (11 12)
- (3) diet/food habits (13 19)
- (4) relationship (20-22)
- (5) psychological well-being and distress (23 30)

The PAGI-QoL questionare contains of 30 items with five subscales: (1) daily activities; (2) clothing; (3) diet/food habits; (4) relationship; and (5) psychological well-being and distress. Each items are scored on a 6-point Likert scale, with response options ranging from 0 (none) to 5 (severe problem all of the time). Subscale scores are calculated by averaging the item responses. A total score is calculated by averaging subscale scores.

Appendix 5 Perioperative protocol

The day before G-POEM (POD-1)

- Fasting for 24 to 48 hours (according the investigator)
- Current weight, QoL, ASA physical status
- Endoscopic examination with event. removal of the remaining food (optional)
- Anesteshiologist's examination
- Blood sampling for: Haemoglobin, WBC, RBC, Thrombocytes, CRP, Quick, Haemoglobin A1c in patients with DM. Other blood tests possible. - may also be done in the morning prior to the procedure ("day 0").
- Liquids up to 20:00 hours, then nil per os
- Supportive infusions according to an attending physician

Day " 0 " (procedure)

- Omeprazole 40 mg iv (or similar PPI) will be given to patients at 6.00 7.00 o'clock and then 3xdaily until the morning on POD 1 (saline only will be given in the sham group). Please, keep patients and hospital staff blinded as much possible.
- 15 to 60 minutes before the procedure, the patients (active group) will be administered intravenous antibiotics: e.g. Ceftriaxone 2 gr (or similar antibiotics) and Metronidazole 500mg. Patients in the sham group will be given placebo (normal saline).
- After the procedure, nil per os for 24 hours (both group).
- Analgesics and anti-emetics as needed.

Day after G-POEM (POD1)

- Morning (6:00 am): last dose of i.v. omeprazole 40 mg in active arm (saline in placebo group), then esomeprazole 2x40 mg (or other PPI) for at least 3 weeks and then on demand for all patients.
- Ceftriaxone 2 gr i.v. (or similar antibiotic), placebo (normal saline) in the sham arm.
- Mucosal integrity will be confirmed with either endoscopy or X-ray with water soluble contrast or both at the discretion of an investigator. *If necessary, additional intervention to close mucosal incision will be used.*
- If no leak or other problems are detected, patients will be allowed to drink clear fluids and begin re-alimentation.
- Analgesics if necessary
- Blood sampling: blood count, coagulation, creatinine, ions, CRP, glycemia
- Discharge from a hospital according to the clinical condition

[figure not shown]
Second day after the procedure (POD2)

- PPI orally all patients
- ATB only, if necessary

Recommendation: After patient's discharge, it is advisable to keep patient's allocation at the Clinic in a closed envelope. I case of need (e.g. urgent visit), the envelope can be opened and a physician on duty has an immediate access to the treatment's allocation.

Appendix 6

Study design

Appendix 7

Center ID and Patient IDs

1. Codification (for CRF)

Appendix 8:

Adverse event (AE) / Serious Adverse Event (SAE) Report Form

Definition: An adverse event is any undesirable, unintentional or unanticipated event that occurs during use of the investigational device, whether or not considered related to the therapy. A serious adverse event (SAE) is an event that is: fatal, life-threatening, results in persistent or significant disability/incapacity, requires or prolongs inpatient hospitalization. SAE must be reported within 24 hours to the Prague study center ([contact], copy: [contact]) and the Ethics Committees/IRB if applicable.

Hospital visits due to follow up visi	ts are not conside	ered to be SAE.	
☐ Initial report			
□ Consecutive report			
Date AE start:///		unexpected event	
Event related to G-POEM / SHAM $\hfill \square$ No	procedure □ Possibly		□ Yes
Complication: □ Perforation	□ Bleeding	□ Infection	□ Other
Please describe complication:			
Intervention required: No please describe intervention:		Yes	
medication required: No medication(s):		Yes	

R	eport	tof	a	Ser	ious	Ad	lvers	se E	lven	t
---	-------	-----	---	-----	------	----	-------	------	------	---

Hospitalization or prolongation	of nospital stay red Yes	uired (SAE): □ No	
If yes, please report within 24 happlicable!	ours to the Prague	e study center and Ethics Committee/IRB	if
Date of hospitalisation/ - prolon	gation(I	DDMMYY)	
Date hospital discharge	(DDMMYY)		
□ event resolved	□ event ongoi	ng	
□ long term sequela	□death	□ unknown	
Description/ comment:			
Date AE ston: / /	(DDMMYY)	

Data and Safety Monitoring Board

IKEM, Department of hepatogastroenterology 8th of February 2021, Prague

Study: A Randomized, Sham and Cross-Over-Controlled Trial of per-oral endoscopic pyloromyotomy (G-POEM) in patients with refractory gastroparesis (GREG)

ClinicalTrials.gov identifier: NCT03356067

Grant number: 17-28797A

To the principal investigator

[name]
Department of hepatogastroenterology
IKEM
[name]

The DSMB met at 29th of January 2021 and reviewed interim results after 41 subjects have been randomized and 33 patients completed the M6 visit. At present, there is a significant difference regarding the main endpoint (treatment success at 6 months) in favor of the active group (vs. sham). Also, 100 % of patients, who had undergone cross-over G-POEM after they underwent a sham procedure, experienced a treatment success. Based on these results, the Committee recommends to stop enrolment now because:

- 1. It would be highly unlikely that during the further course of the study, the results would change qualitatively. The p-value of the logistic regression analysis comparing the treatment success between G-POEM and sham groups is equal to p=0.003. Since no interim stopping scheme with pre-specified corrected alpha thresholds was specified, we primarily consider the Haybittle–Peto boundary. This boundary states the critical value of p=0.001 at all interim analyses and sometimes p=0.002 is used if only one interim analysis is performed. Our obtained p-value does not directly reach this level of significance, but taking into account the heuristic nature of the Haybittle–Peto approach and the fact that this approach is considered very conservative for stopping a trial, we believe that the evidence in favor of G-POEM efficacy is sufficient for stopping further enrollment.
- Even if the strict statistical threshold for early trial termination is not met, ethical reasons should be considered. In particular, the risks related to general anesthesia in the sham procedure can not be further justified in the light of the current results. The Board consider it unethical to continue with study enrolment.

There should be further studies assessing the key question of how to select patients who will benefit from G-POEM, but we believe that there is no need for further inclusion of sham procedures.

Data and Safety Monitoring Committee members:

Chairperson:

MUDr. [name] – gastroenterologist

Head physician

MEDIENDO s.r.o.

[name]

MUDr. [name] – gastroenterologist

MUDr. [name] - hepatologist

MUDr. [name] – gastroenterologist and hepatologist

MUDr. [name] - neurologist, independent specialist

Mgr. [name] – statistician

MUC. [name] - medical student

JUDr. [name] - lawyer

In Prague, 8th of February 2021

MUDr. [name]

Head physician

MEDIENDO s.r.o.

[name]

[name]

Mediendo s.r.o.
Gastroenterologie, odb. 105
[name]
[name]

[contact]

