- 1. Proportion of patients with treatment success in the active arm at 3M, 12M, 24M and 36M.
- 2. Proportion of patients with treatment success in the sham group at 3M.
- **3.** Change in GSCI and PAGI-SYM before and after G-POEM at 3, 6, 12, 24 and 36M and before vs. after sham procedure at 3M and 6M; comparison of the change of the scores between the active and sham groups.
- **4.** Proportion of patients (randomized into the sham group and undergoing G-POEM after 6M) with treatment success after the sham procedure (6M) and after G-POEM (6M) cross over part
- **5.** Change in GSCI and PAGI-SYM before and after G-POEM vs. sham procedure in patients randomized to the sham group at 3 and 6M (cross over part)
- 6. Subgroup post-hoc analyses of the treatment success and change in symptomatic scores according to etiology of gastroparesis.
- 7. Change in gastric emptying (scintigraphy) study, EndoFLIP values and/or gastric emptying breath test before and after both G-POEM and sham procedure; comparison of the mean change of these parameters between active and sham groups.
- **8.** Procedure details (length of the procedure, technical success, perioperative adverse events).
- 9. Short- and long-term adverse events.

11. Sample size calculation

A total of 86 patients will be randomized.

- 43 patients will be randomized into the G-POEM group
- 43 patients will be randomized into sham group

Sample size calculation is based on expected therapeutic success of G-POEM in 50% of patients vs. 20% in the sham group; significance level 0,05; study power 0,8; beta error 0,2; adjustment for 15% expected drop out.

12. Statistical analysis

Data will be analyzed for both the intention to treat (ITT – a cohort for primary end point analysis) and the per-protocol population (sensitivity analysis). The per-protocol analysis will include only patients who will complete the entire follow-up. The efficacy of G-POEM at month 6 (main outcome) will be evaluated by Poisson regression with robust standard errors or similar regresion based approach. Baseline characteristics will be compared by using chi-squared tests for categorical variables and t-tests for continuous data.

The efficacy of treatment at other time points (3M, 12M, 24M and 36M) as well as the pooled efficacy cross-over + active groups will be evaluated similarly.

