15.4. Administrative Aspects and Adverse Events recording

Patients will be coded using a numeric randomization code (anonymized) and only anonymized data will be submitted to the PI site (Prague) for data management. Adverse events (AE) and serious adverse events (SAE) (**Appendix 8**) will be reported to the coordinating study centre and there to the DSMB and the study steering committee (see below) to control safety issues and to discuss intervention or protocol amendments accordingly. An adverse event is any undesirable event that occurs whether or not considered to the participation in the study. Therefore, AEs can be any undesirable, unintentional, or unanticipated outcome or symptom or any disease in a timely relation to the study participation, independent of a suspected relation.

AE will be documented on designated CRF forms. A serious adverse event is defined as any event within the study timeframe fulfilling at least one of the following criteria:

- Death
- Live-threatening event
- Hospitalisation (required or prolonged)
- Event that results in disability
- Any event that an intervention to prevent one of the points above...

According to ICH-GCP guidelines, SAE(s) have to be reported within 24hours by email ([contact], copy: [contact]). SAE have to be reported to the local ethics committee of the study site.

CRFs as well as all study related documents will be kept at least 10 years after study termination. Any study subject is allowed to withdraw her / his consent for study participation at any time for any given reason.

16. References

- 1. Revicki, D.A., et al., Gastroparesis Cardinal Symptom Index (GCSI): development and validation of a patient reported assessment of severity of gastroparesis symptoms. Qual Life Res, 2004. 13(4): p. 833-44.
- 2. Jung, H.K., et al., *The incidence, prevalence, and outcomes of patients with gastroparesis in Olmsted County, Minnesota, from 1996 to 2006.* Gastroenterology, 2009. 136(4): p. 1225-33.
- 3. Dickman, R., et al., Gender aspects suggestive of gastroparesis in patients with diabetes mellitus: a cross-sectional survey. BMC Gastroenterol, 2014. 14: p. 34.
- 4. Langworthy, J., H.P. Parkman, and R. Schey, *Emerging strategies for the treatment of gastroparesis*. Expert Rev Gastroenterol Hepatol, 2016. 10(7): p. 817-25.
- 5. Davis, B.R., et al., *The Long-Term Efficacy and Safety of Pyloroplasty Combined with Gastric Electrical Stimulation Therapy in Gastroparesis.* J Gastrointest Surg, 2016.

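### Appendix 8 ties adverse events to use of an undefined device and omits the intervention criterion for serious events, in conflict with Section 15.4

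*Protocol*

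**What the plan says.** Section 15.4 defines an adverse event broadly: "An adverse event is any undesirable event that occurs whether or not considered to the participation in the study". It extends this to "any disease in a timely relation to the study participation, independent of a suspected relation". For serious events it says: "A serious adverse event is defined as any event within the study timeframe fulfilling at least one of the following criteria". Five criteria follow: death, threat to life, hospitalisation, disability, and a last one that breaks off: "Any event that an intervention to prevent one of the points above". Section 15.4 refers to Appendix 8 for both kinds of event and sends both to the coordinating centre, and from there to the DSMB and the steering committee. On ethics reporting it is unconditional: "SAE have to be reported to the local ethics committee of the study site".

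Appendix 8 is the report form and carries its own definitions. Its adverse-event definition begins: "An adverse event is any undesirable, unintentional or unanticipated event that occurs during use of the investigational device". It goes on to say that the event need not be thought related to the therapy. Its list of serious events has four criteria: death, threat to life, disability that is lasting or significant, and hospital admission or a longer stay. It asks for ethics-committee notification only where applicable.

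Section 10.2 makes "Short- and long-term adverse events" the ninth secondary outcome. Follow-up runs to 36 months.

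**The concern.** Two definitions of the same thing stand in one protocol, and no text says which one governs. Sites classify events with the form in front of them, and that form has the narrower wording. The trial names ten recruiting countries, so different sites could apply different rules in good faith.

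Three uses of the data depend on the classification. Safety is part of the study aim (Section 5). Adverse events are a secondary outcome. The statistical analysis plan within Section 12 says that analysis of adverse events could end the study. If one site follows Section 15.4 and another follows the form, the count of serious events is not one quantity.

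**Working it through.** The plan states no figure on this point, so the check is a comparison of texts.

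| Element | Section 15.4 | Appendix 8 |
|---|---|---|
| Scope of an adverse event | Time relation to study participation | Use of the investigational device |
| Number of seriousness criteria | 5 | 4 |
| Intervention criterion | Present, wording unfinished | Absent |
| Disability | "Event that results in disability", without qualifier | Must be lasting or significant |
| 24-hour reporting | All serious events | All events serious under its own list |
| Ethics committee | Mandatory | Where applicable |

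**Step 1: the device wording.** The intervention is an endoscopic procedure compared with sham, and the protocol does not say what the investigational device is. Taken literally, the phrase ends the adverse-event period with the procedure. Section 15.4 and the long-term part of secondary outcome 9 both require events after that.

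**Step 2: the form against itself.** The form asks whether the event is related to G-POEM or to the sham procedure. It says that hospital visits for follow-up are not serious events. It also has entries for continuing events and long-term sequelae. These fields make sense only if the form is used in both arms and after the procedure, so its definition contradicts its own fields.

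**Step 3: which events are classified differently.**
- A complication that threatens life, prolongs the stay or leaves significant lasting disability is serious under both texts.
- A complication during the procedure that is treated endoscopically, with none of those consequences, is an adverse event under both texts. Under the apparent intent of the fifth criterion in Section 15.4 it can be serious. Under Appendix 8 it is not.
- An event first arising months after discharge is an adverse event under Section 15.4. Under the literal definition in Appendix 8 it is not one at all.

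**Step 4: whether the second kind can occur.** The protocol foresees clipping of mucosal injuries during G-POEM. It also foresees further closure of the incision on the day after, with discharge possible on that day or the next (Section 9). An endoscopic intervention within the planned stay is therefore possible. Whether such a step counts as an event under Section 15.4 cannot be settled while the fifth criterion is unfinished.

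**Step 5: scale.** No event rates are given. As arithmetic only, one reclassified event shifts the serious-event proportion in an arm of the planned size by 1/43 = 2.3 percentage points. The DSMB letter recommended stopping enrolment at 41 randomised. If allocation was close to equal (an assumption), that is 20 or 21 per arm, and one event is 1/21 = 4.8 to 1/20 = 5.0 points. These are the sizes of one step, not estimates of how many events are affected.

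**The case against.** The strongest reply is that the consequences are small. Several parts of it stand.

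- A reader might infer that treated complications go unreported. The documents do not support that. The form has boxes for perforation, bleeding and infection, and an item on the intervention required. Section 15.4 sends non-serious events to the DSMB as well. What is at stake is the seriousness label, the 24-hour deadline and ethics-committee notification.
- A reader might infer that the form asks for rapid reporting only when there is a hospital stay. Its single yes/no seriousness prompt does concern hospitalisation, but its header applies the 24-hour rule to every event that it defines as serious.
- A reader might infer that late events and sham-arm events are in fact excluded. That follows only from one phrase, and the fields described in step 2 point the other way.
- A reader might infer that the loss falls mainly on G-POEM. For the intervention criterion this is plausible, since only G-POEM involves incision and myotomy, but it remains inference. The device wording affects late events in both arms and, read literally, might exclude more in the sham arm. No net direction follows.
- The fifth criterion in Section 15.4 has no verb, so calling an event serious under it relies on its evident intent.

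The contradiction itself is not answered. Both definitions are stated in the protocol and they differ, so this is not detail that could be left to a separate analysis plan.

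**Conclusion.** The point holds as an internal contradiction worth correcting. Appendix 8 is narrower than Section 15.4 for adverse events and for serious adverse events. Its literal definition cannot deliver secondary outcome 9 and does not fit the form's own fields.

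The practical gap has two parts. Late events could be left out by a site that follows the definition literally. A complication treated endoscopically, without a longer stay, threat to life or disability, could be recorded as non-serious and so miss 24-hour and ethics-committee reporting.

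The second part assumes that the unfinished criterion in Section 15.4 was meant to cover events needing an intervention to prevent a serious outcome. The size and direction of any difference between arms cannot be stated from the documents. The primary outcome and its analysis are unaffected.

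**What to change.** Reconcile Appendix 8 with Section 15.4:

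- Use one adverse-event definition that covers the whole study period in both arms, and remove the device-use wording.
- Use one list of seriousness criteria in both places, with the fifth criterion in Section 15.4 completed and the disability wording made the same.
- Bring the form's conditional ethics-committee wording into line with the mandatory reporting in Section 15.4.
- Make the form's seriousness prompt list every criterion.
- Re-check the forms already filed against the reconciled definition. This remains useful after enrolment stops, because follow-up continues.

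The cost is a form revision, a review of filed forms and possible reclassification of a few events as serious.
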